11.7. Analysis of demographics

Demographic characteristics (age at the first dose in years, gender, geographical ancestry, smoking status) and cohort description will be summarised by group using descriptive statistics:

- Frequency tables will be generated for categorical variable such as gender; geographical ancestry, age category, smoking status;
- Mean, median and standard deviation will be provided for continuous data such as age.

The distribution of subjects enrolled among the study sites will be tabulated as a whole and per group.

Withdrawal status will be summarised by group using descriptive statistics:

- The numbers of withdrawn subjects will be tabulated according to the reason for withdrawal;
- The number of subjects enrolled into the study as well as the number of subjects excluded from ATP analyses will be tabulated.

No inferential analyses of demographic data are planned.

11.8. Analysis of efficacy

The primary analysis will be performed on the mTVC and repeated on the TVC **and the FAS**. The primary analysis will also be repeated on the efficacy ATP (per-protocol) cohort if the percentage of vaccinated subjects excluded from the ATP cohort for efficacy is more than 5%.

Efficacy – Clinical Endpoint

The following incidence rates of AECOPD (any type) occurring from enrolment up to 1 month post-Dose 2 will be computed together with **95% CI**, and incidence rates together with VE in the prevention of AECOPD (any type) will be computed over a period starting 1 month post-Dose 2 and lasting for 1 year, with **95% CI**:

- All-cause moderate and severe AECOPD (primary endpoint).
- All-cause, all-severity AECOPD.
- All-cause AECOPD, by severity.

For the primary endpoint, the 87% CI will also be reported in order to evaluate the null hypothesis at 13% alpha level (2-side). This objective will be considered a success if the lower limit of the 87% CI will be above 0%. (Amended 27 March 2019)

The CIs of the incidence rate will be computed using a model which accounts for repeated events. The primary outcome will be analysed using the Negative Binomial regression model with number of AECOPD as dependent variable; treatment (vaccine or placebo), age group (40–59 years or 60–80 years), GOLD grade (2, 3 or 4), history of exacerbations (<2 or ≥ 2) and country as independent variables, with logarithm as link function, and the logarithm of time for follow-up (in years) as an offset variable. If the model does not converge, the Poisson distribution will be used instead of the Negative Binomial one.

VE for AECOPD events is defined as:

$$VE(\text{AECOPD}) = 1 - R_{\text{vacc}} / R_{\text{con}}$$

with:

- R_{vacc} = average yearly incidence rate of AECOPD events per subject in the group 10-10-3-AS.
- R_{con} = average yearly incidence rate of AECOPD events per subject in the Control group.

Incidence rates of AECOPD (any type) and VE, together with 95% CI, will be computed for the following time periods:

- At Month 3, 6, 9, 12, 15 from Day 1 (cumulative)
- By 6 Months follow up period (from 1 month post-Dose 2)
- By 3 Months follow up period (from 1 month post-Dose 2)

The model used will be the same as for the primary analysis.

A sensitivity analysis **using** a permutation test will be performed for the primary efficacy endpoint.

Efficacy – Bacteriological Endpoint (PCR)

Similarly, VE in prevention of NTHi and/or Mcat associated AECOPD, over a period starting 1 month post-Dose 2 and lasting for 1 year and its 95% CI will be computed, with the following incidence rate:

- NTHi-associated moderate and severe AECOPD.
- NTHi-associated all-severity AECOPD.
- NTHi-associated AECOPD, by severity.
- Mcat-associated moderate and severe AECOPD.
- Mcat-associated all-severity AECOPD.
- Mcat-associated AECOPD, by severity.
- NTHi and/or Mcat-associated moderate and severe AECOPD.
- NTHi and/or Mcat-associated all-severity AECOPD.
- NTHi and/or Mcat-associated AECOPD, by severity.
- The time until first moderate and severe AECOPD.
- The time until first AECOPD (any severity).
- The time until first AECOPD by severity.

The proportion of sputum samples with exact 95% CI obtained at each visit (scheduled visits and AECOPD-driven visits) and positive for bacterial pathogens (overall and by bacterial pathogen) will be computed by group and overall. The exact CIs will be estimated assuming independence of bacterial results across sputum samples.

Incidence rates of AECOPD associated to NTHi and/or Mcat, and VE, together with 95% CI will be evaluated for the following time periods:

- At Month 3, 6, 9, 12, 15 from day 1 (cumulative)
- At 6 months follow up period (from 1 month post-Dose 2)
- At 3 months follow up period (from 1 month post-Dose 2)

The model used will be the same as for the primary analysis. All above analyses will be performed in sputum samples using PCR. (Amended 27 March 2019)

Efficacy – Bacteriological Endpoint (culture)

Same set of analyses, as in the bacteriological efficacy endpoints, will be performed in the subset of culture sputum data.

Incidence rates of AECOPD associated to NTHi and/or Mcat, and VE, together with 95% CI will be evaluated for the following time periods:

- At Month 3, 6, 9, 12, 15 from day 1 (cumulative)
- At 6 months follow up period (from 1 month post-Dose 2)
- At 3 months follow up period (from 1 month post-Dose 2)

The model used will be the same as for the primary analysis. All above analyses will be performed in sputum samples using PCR. (Amended 27 March 2019)

Bacteriological load

The following will be performed in PCR and culture samples:

- Percentage of subjects with *H. influenzae* and *M. catarrhalis* in sputum before first vaccination and at Day 91, Day 181, Day 271, Day 361 and Day 451, per group.
- Relative abundance of *H. influenzae* and *M. catarrhalis* in sputum as measured by culture before first vaccination and at Day 91, Day 181, Day 271, Day 361 and Day 451 and at each AECOPD visit, per group.
- Descriptive summaries of the presence and quantity of NTHi and/or Mcat and/or other bacteria at each planned visit will be provided for both culture (semi-quantitative estimation) and PCR analysis (copies/mL).

Acquisition and apparition

The following definitions will be used:

- ***Acquisition: The first time a bacterium is detected in the sputum of a patient over the course of the study visits (a positive status at the visit considered as baseline excludes a subject from this analysis).***
- ***Apparition: Detection of a bacterium in the sputum of a patient taken during a study visit which was not detected in the sputum taken during the previous visit.***

The following analyses will be performed for (NT)Hi (alone or with other bacteria), MCAT (alone or with other bacteria) and either Hi or MCAT:

- ***Percentages of subjects with acquisition for each treatment group and risk ratio between groups, considering both Day 1 and Day 91 as baseline.***
- ***Percentages of subjects with apparition for each treatment group and risk ratio between groups, considering Day 1 as baseline.***

- *Percentages of subjects with acquisition at AECOPD visit for each treatment group and risk ratio between groups, considering both Day 1 and Day 91 as baseline.*
- *Percentages of subjects with apparition at AECOPD visit (when negative at previous stable visit) for each treatment group and risk ratio between groups, considering Day 1 as baseline*
- *Frequency table for apparition (number of apparition for each subject from Day 1), by treatment groups.* (Amended 27 March 2019)

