5.2. Inclusion criteria for enrolment

Deviations from inclusion criteria are not allowed because they can potentially jeopardize the scientific integrity, regulatory acceptability of the study or subject safety. Therefore, adherence to the criteria as specified in the protocol is essential.

All subjects must satisfy ALL the following criteria at study entry:

- Subjects who, in the opinion of the investigator, can and will comply with the requirements of the protocol (e.g. electronic Diary Card completion, number of blood draws, sputum sampling, pre- and post-bronchodilator spirometry, return for follow-up visits).
- Written informed consent obtained from the subject prior to performing any study specific procedure.
- A male or female between, and including, 40 and 80 years of age at the time of the first vaccination.
- Confirmed diagnosis of COPD (based on post-bronchodilator spirometry) with forced expiratory volume in 1 second (FEV1) over forced vital capacity (FVC) ratio (FEV1/FVC) < 0.7, AND FEV1 < 80% predicted (GOLD 2, 3 and 4).
- Current or former smoker with a cigarette smoking history of ≥ 10 pack-years.
Refer to the [glossary of terms](#) for the definitions of pack-years and of current and former smoker.

- Stable COPD patient* with documented history** (e.g. medical record verification) of at least 1 moderate or severe AECOPD within the 12 months before Screening.

* Patient for whom the last episode of AECOPD is resolved for at least 30 days at the time of first vaccination.

** A documented history of a COPD exacerbation (e.g. medical record verification) is a medical record of worsening COPD symptoms that required systemic/oral corticosteroids and/or antibiotics (for a moderate exacerbation) or hospitalization (for a severe exacerbation). Prior use of antibiotics alone does not qualify as an exacerbation history unless the use was associated with treatment of worsening symptoms of COPD, such as increased dyspnea, sputum volume, or sputum purulence (color). Subject verbal reports are not acceptable.

Refer to the Study Procedures Manual (SPM) for additional details on what is accepted as documented history of AECOPD. Refer to [Table 1](#) for the definitions of moderate and severe AECOPD.

- Capable of complying with the daily electronic Diary Card completion throughout the study period, according to investigator's judgement at Visit 1.

Refer to the SPM for recommendations on what is considered adequate compliance by Visit 1.

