6.2.2.2. Treatment allocation to the subject

The treatment numbers will be allocated by dose.

6.2.2.2.1. *Study group and treatment number allocation*

The target will be to enrol approximately 600 eligible subjects who will be randomly assigned to two study groups in a (1:1) ratio (approximately 300 subjects in each group).

Allocation of the subject to a study group at the investigator site will be performed using a randomisation system on internet (SBIR). The randomisation algorithm will use a minimisation procedure accounting for age (40 - 59 years or 60 - 80 years), number of moderate/ severe AECOPD in the previous year (< 2 or ≥ 2), GOLD grade (GOLD 2, GOLD 3 or GOLD 4) and country. Minimisation factors will have equal weight in the minimisation algorithm.

Details on the minimisation algorithm are reported in the statistical analysis plan.

At Visit 1, before administration of vaccine Dose 1 to eligible subjects who signed and dated the ICF at the Screening Visit, the study staff in charge of the vaccine administration will access SBIR. Upon providing the subject's age category (40 - 59 years or 60 - 80 years), number of moderate/ severe AECOPD in the previous year, his/ her GOLD grade and subject identification number, the randomisation system will determine the study group and will provide the treatment number to be used for the first dose.

The number of each administered treatment must be recorded in the eCRF on the Vaccine Administration screen.

When SBIR is not available, please refer to the SBIR user guide or the Study Procedures Manual (SPM) for specific instructions.

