6.9.3. Record history of moderate and severe AECOPD within the previous year

Obtain the subject's history of moderate and severe AECOPD within the previous year.

At Screening, subjects need documentation for at least 1 moderate or severe AECOPD within the previous year to be eligible for study participation.

At Visit 1, both documented (by medical record review) and self-reported, non-documented moderate and severe AECOPD within the year before Visit 1 should be recorded in the eCRF. The total number of moderate and severe AECOPD (including self-reported, non-documented AECOPD) will be entered in SBIR for randomisation.

Refer to the SPM for details on recording of moderate and severe AECOPD within the previous year.

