11.4. Determination of sample size

Primary objective - Efficacy: All (causes) of moderate and severe AECOPD

The primary objective of this study is to assess the efficacy of the investigational vaccine as compared to placebo control, as measured by the rate of moderate and severe AECOPD from 1 month after second dose of vaccination till 1 year after. Sample size is computed based on the probability to detect a clinically relevant effect. Sample size is estimated using a formula from [Keen, 2007]. Assuming a yearly incidence rate of moderate and severe AECOPD in the placebo arm equal to 0.8 per subject [Mackay, 2012; Dransfield, 2013] and an over-dispersion parameter of 1.8, ~300 subjects per group will provide 80% power to detect at least a 28% reduction in the rate of AECOPDs in the vaccinated group compared to the placebo group, with a 1-sided 6.5% significance level and a dropout rate of 15%.

Table 23 presents sample size under different assumption for over-dispersion parameter and AECOPD incidence rate in placebo arm, assuming a VE=28%, a drop-out of 15% (85% of enrolled subjects are expected to complete one year follow up) and 1:1 randomization ratio.

Table 23 Total number of subjects for primary endpoint

Overdispersion factor*: 1.8				
2-side α -level	Rate in Placebo	Rate in Treatment	N per group	Total Sample size**
13%	0.9	0.648	228	536
10%	0.9	0.648	254	596
13%	0.8	0.576	257	604
10%	0.8	0.576	286	672
13%	0.7	0.504	293	690
10%	0.7	0.504	327	768
13%	0.6	0.432	342	804
10%	0.6	0.432	381	896
Overdispersion factor*: 2				
13%	0.9	0.648	251	590
10%	0.9	0.648	280	658
13%	0.8	0.576	282	664
10%	0.8	0.576	314	740
13%	0.7	0.504	323	760
10%	0.7	0.504	360	846
13%	0.6	0.432	376	886
10%	0.6	0.432	419	986

Sample size calculated from a formula from Keen, 2007 implemented on SAS.

* Overdispersion factor for a Poisson distribution.

**Total sample size takes in to account 15% drop-out rate.

Secondary objective - Efficacy: mild and moderate AECOPD associated to bacteriological pathogens (PCR).

One of the secondary objectives is to assess efficacy of the investigational vaccine compared to placebo, as measured by the rate of moderate and severe AECOPD associated to NTHi and/or Mcat (detected by PCR), starting from 1 month after second dose of vaccination till 1 year after.

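### The primary model adjusts for exacerbation history only as <2 versus ≥2 although the prior-year count is recorded for every randomised subject: a small, avoidable loss of precision

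*Protocol*

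**What the plan says.** Section 11.8 sets out the primary model in full: "The primary outcome will be analysed using the Negative Binomial regression model with number of AECOPD as dependent variable", with a log link, log follow-up time as offset, and treatment and the four minimisation factors as covariates. The covariate list includes "GOLD grade (2, 3 or 4), history of exacerbations", and history enters as "history of exacerbations (<2 or ≥ 2) and country as independent variables". Section 6.2.2.2 uses the same factor with the same cut in the minimisation. Section 11.8 also carries the primary model over to the analyses by time period and to the bacteriological analyses.

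Section 6.9.3 asks for more than the category. Both documented and self-reported "moderate and severe AECOPD within the year before Visit 1 should be recorded in the eCRF", and "The total number of moderate and severe AECOPD (including self-reported, non-documented AECOPD) will be entered in SBIR for randomisation". Eligibility under Section 5.2 is a separate requirement: a documented history "of at least 1 moderate or severe AECOPD within the 12 months before Screening".

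The coding is therefore fixed in the protocol itself, not left to the statistical analysis plan.

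**The concern.** The category of two or more pools subjects with two, three, four and more prior-year events. Section 1.1.1 notes that exacerbation rates differ greatly between patients, and the sample size assumes an overdispersion of 1.8. Prognostic information inside the upper category is collected but not used. Whatever it could explain stays in the dispersion term and widens the interval for VE. Success is judged on whether the lower limit of the 87% interval lies above 0%, so a wider interval costs some power. The data needed to narrow it are already in the eCRF.

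**Working it through.** **Inputs from Section 11.4.** Placebo rate 0.8 per year, VE 28% (vaccine rate 0.576), overdispersion 1.8, two-sided alpha 13%, power 80%, dropout 15%, 1:1 allocation.

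**1. The plan's own sample size.** Take k = (1.8 − 1)/0.8 = 1.0 and the negative binomial formula

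n per group = (z₀.₉₃₅ + z₀.₈₀)² × (1/μ₀ + 1/μ₁ + 2k) / [ln(μ₁/μ₀)]²

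- (1.514 + 0.842)² = 5.55
- 1/0.8 + 1/0.576 + 2 = 1.25 + 1.74 + 2.00 = 4.99
- [ln 0.72]² = 0.1079
- n = 256.4, against 257 in Table 23. The total is 2 × 257/0.85 = 604.7, against 604.

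All 16 entries for N per group in Table 23 reproduce in this way. With 300 × 0.85 = 255 evaluable per group, power is 79.8%. The formula contains no covariate term, so the stated 80% does not depend on how history is coded.

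**2. Where a covariate could help.** The term 2k is 2.00 of 4.99, about 40% of the variance of the log rate ratio. Only that part can be reduced by a prognostic baseline variable, and the category already takes some of it.

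**3. Size of the gain.** The protocol gives neither the distribution of prior-year counts nor its link to the trial-year rate, so both had to be assumed. In four simulated scenarios each subject has a gamma-distributed rate, a prior-year count of at least 1, and a trial-year rate that also varies from year to year. The outcome is calibrated to a rate of 0.8 and k = 1, with 255 per arm and 600 trials per scenario. The table compares the category with log(count) used in its place. Power is Φ(0.3285/SE − 1.514), with 0.3285 = |ln 0.72|.

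| Share with 1 / 2 / 3 / ≥4 prior events (%) | Mean SE, category | Mean SE, log count | Variance cut | Power (%) |
|---|---|---|---|---|
| 45 / 27 / 14 / 14 | 0.1358 | 0.1346 | 1.8% | 81.7 → 82.3 |
| 50 / 25 / 13 / 13 | 0.1347 | 0.1323 | 3.5% | 82.2 → 83.4 |
| 35 / 24 / 16 / 25 | 0.1351 | 0.1319 | 4.7% | 82.0 → 83.6 |
| 44 / 24 / 13 / 19 | 0.1332 | 0.1282 | 7.4% | 82.9 → 85.3 |

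The variance cut is 1 − (SE ratio)². In the first row, for example, it is 1 − (0.1346/0.1358)² = 1.8%. Its inverse gives an effective sample size gain of about 2% to 8%, or roughly 10 to 50 of 600 subjects. The directly counted success rates are noisier, with a simulation error of √(0.82 × 0.18/600) = 1.6 points each. They were 81.8, 81.7, 81.3 and 82.0% with the category, and 81.7, 85.2, 81.7 and 85.3% with log count. The first scenario thus shows no visible gain by that measure.

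A separate simulation of the model proposed below (category plus log count, including a version capped at 4) gave a variance cut of about 1% to 6% at moderate dispersion, and up to 8% at the highest dispersion tried. That is worth roughly 0.2 to 2 power points.

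**4. Validity.** With VE set to 0% (400 trials per scenario), one-sided rejection was 4.0% to 7.2% under either coding. The nominal level is 6.5% and the simulation error about 1.2 points, so neither coding shows inflation.

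**5. Can the count be zero?** Eligibility looks back 12 months from Screening, whereas the recorded count looks back one year from Visit 1. Table 8 places Visit 1 6 to 29 days after Screening, and later after a re-screening visit. A subject whose only event fell at the start of the eligibility window can have a count of 0 at Visit 1. An event between Screening and Visit 1 would not refill the count, because Section 6.6 makes that subject a screening failure. The scenarios in step 3 contain no zeros, so they do not test this case.

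**The case against.** The strongest reply is that nothing here is wrong. Adjusting for the allocation factors in the form used for allocation is a standard pre-specified choice, the power claim is met without it, and the gain is small and rests on assumptions. All of that stands, and it limits the point to efficiency.

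The count is also an imperfect measure. Section 6.9.3 includes self-reported, undocumented events, while Section 5.2 refuses verbal reports for eligibility. Distinctions such as three versus five are where recall error would matter most, and the cut at two is less exposed to it. This stands as well and favours the lower end of the range.

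Three stronger readings are tempting, and the documents do not support them:

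- A reader might infer that fewer than two means exactly one, given the entry requirement. The two look-back windows differ, so zero is possible. A plain log(count) would then be undefined and could drop subjects from the primary analysis.
- A reader might infer that the binary term biases VE or leaves the trial short of its stated power. Steps 1 and 4 show otherwise.
- A reader might read the overdispersion of 1.8 as stable subject differences that a prior-year count would largely explain, and so expect a large gain. Table 23 labels it only as an overdispersion factor for a Poisson distribution. The protocol does not say how much of it persists from year to year.

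**Conclusion.** The point holds as a minor efficiency improvement. The primary model uses a two-level version of a baseline count that is recorded for every randomised subject. The expected gain from using the count is a few percent of the variance of the log rate ratio and about 0.5 to 2.5 percentage points of power. The lower end is more likely if self-reported counts are noisy, and the add-on model fell to about 0.2 points in its least favourable setting. These figures depend on assumed count distributions and year-to-year stability that the protocol does not give. The planned analysis remains valid if nothing is changed.

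**What to change.** Before unblinding, amend the model in Section 11.8. Keep the four minimisation factors as they are and add one continuous covariate, for example log(max(count, 1)), with the upper cap stated in advance. This form is zero for counts of 0 or 1, so the category sets the step at two events and the new term acts only within the group with two or more. Report the model with the category alone as a sensitivity analysis. State whether the added term also applies to the time-period and bacteriological analyses that borrow the primary model.

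The cost is one parameter, an assumed log-linear form above two events, and some noise from self-reported events. No new data, visits or subjects are needed.

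### The Poisson fallback names no variance correction, so if it is used while the planned overdispersion is present, the 87% CI that decides success is too narrow

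*Protocol*

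**What the plan says.** Protocol Section 11.8 sets the primary model: "The primary outcome will be analysed using the Negative Binomial regression model with number of AECOPD as dependent variable". Treatment, age group, GOLD grade, exacerbation history and country are covariates, the link is logarithmic, and log follow-up time is the offset. The same paragraph wants the intervals to come from a model that allows for repeated events in a subject. It then gives the contingency: "If the model does not converge, the Poisson distribution will be used instead of the Negative Binomial one". No scale parameter, quasi-likelihood, robust variance or intermediate step follows.

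The decision rule is in the same section: "This objective will be considered a success if the lower limit of the 87% CI will be above 0" percent. Sections 11.8 and 11.11 put the test at a two-sided 13% level, which is one-sided 6.5%. A permutation test is also planned for the primary endpoint, but only as a sensitivity analysis.

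Section 11.4 plans for "an over-dispersion parameter of 1.8", and Table 23 adds scenarios with a factor of 2. A footnote to that table defines the factor relative to a Poisson distribution.

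For the analyses by time period and by pathogen, Section 11.8 states: "The model used will be the same as for the primary analysis". The fallback goes with the model.

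**The concern.** An ordinary Poisson model fixes the variance at the mean. The protocol's own planning says that the variance is 1.8 to 2 times the mean, because some patients exacerbate far more often than others. An analyst who follows the fallback literally would report model-based Poisson intervals, and these are too narrow when such heterogeneity is present.

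For the primary endpoint this is more than a reporting matter, because one confidence limit decides whether the proof of concept is declared. An interval that is too narrow makes it easier for the lower limit to clear zero, so the error favours a declaration of efficacy.

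**Working it through.** **Inputs.** Section 11.4: "Assuming a yearly incidence rate of moderate and severe AECOPD in the placebo arm equal to 0.8 per subject"; efficacy 28%, hence a vaccine rate of 0.576; overdispersion factor φ = 1.8; power 80%; 1:1 allocation; "with a 1-sided 6.5% significance level and a dropout rate of 15" percent. The critical value is z(0.935) = 1.514, and z(0.80) = 0.842.

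**Step 1: reproduce the sample size, to establish what φ means.**
- Negative Binomial dispersion: k = (φ − 1)/rate = (1.8 − 1)/0.8 = 1.0.
- n per group = (1.514 + 0.842)² × (1/0.8 + 1/0.576 + 2k) / [ln(0.576/0.8)]² = 256.4, against 257 in Table 23.
- Total with 15% dropout: 2 × 256.4/0.85 = 603.3, against 604.

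The other rows of Table 23 also agree to within one subject per group. A scaled-Poisson formula, φ × (1/0.8 + 1/0.576), gives 276.4 and does not match. So the planned variance is Negative Binomial with k = 1.0, which is 1.8 times the mean in the placebo arm.

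**Step 2: standard error under the fallback, no vaccine effect, rate 0.8 in both arms.**
- Variance per subject on the log-rate scale, Negative Binomial: 1/0.8 + 1 = 2.25.
- The same, Poisson: 1/0.8 = 1.25.
- Ratio of standard errors: √(1.25/2.25) = 1/√1.8 = 0.745.

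**Step 3: consequence for the decision.**
- One-sided false success = 1 − Φ(1.514/√φ).
- True coverage of the nominal 87% CI = 2Φ(1.514/√φ) − 1.

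| φ | CI width / correct width | True coverage | One-sided false success |
|---|---|---|---|
| 1.0 | 1.000 | 87.0% | 6.5% |
| 1.5 | 0.816 | 78.4% | 10.8% |
| 1.8 | 0.745 | 74.1% | 12.95% |
| 2.0 | 0.707 | 71.6% | 14.2% |

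The row for 1.5 allows for covariates that absorb part of the overdispersion.

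**Step 4: check by simulation under the null.** There were 600 subjects with gamma frailty, the model covariates and 15% dropout. Covariate effects, number of countries and dropout timing were assumed, since the protocol does not give them. At k = 1.0, unscaled Poisson declared success in 12.5% of trials with covariate effects and 12.3% without; Negative Binomial did so in 6.5% in both cases. Pearson scaling brought Poisson back to 6.3–6.8%. In a separate run with 255 subjects per arm, a sandwich variance gave 6.1%.

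**Step 5: how often the fallback would be reached.**
- Negative Binomial converged in all 3,000 null trials at k = 1.0 and in all 1,000 at k = 0.75.
- With no overdispersion (k = 0), 260 of 600 runs failed to converge or ended with the dispersion at its boundary. The Poisson error over all those runs was 6.3%, so nothing was lost.
- With overdispersion as planned, failures appeared when a country was forced to have no events: 11–13% of runs with a five-subject country and 25% with a 20-subject country (eight countries assumed).
- The chance that a country of m subjects has no events at rate 0.8 and k = 1 is (1/1.8)^m, which is 5% for m = 5 and 0.3% for m = 10. For one five-subject country the product is about 5% × 13% = 0.7%.

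**The case against.** The strongest objection is that the fallback will almost never operate when it could do harm. Step 5 supports this: failure was common where Poisson is the right model, and at the planned dispersion it occurred only in data forced to contain an empty country. A reader might infer from 13% against 6.5% that the trial's false-success rate doubles. The documents do not support that. The figure needs both non-convergence and overdispersion near 1.8, and under the planning assumptions the two should seldom coincide.

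A reader might also expect the worst damage in the sparse analyses by severity and pathogen, which reuse the model. That does not follow either. With k held at 1, the overdispersion factor is 1 + k × rate, so it falls as events become rarer. For NTHi or Mcat events at 40% of 0.8 (25% plus 15%, taken as not overlapping), the rate is 0.32 and the factor 1.32. A nominal 95% CI then covers 2Φ(1.96/√1.32) − 1, about 91%. Section 11.11 also makes these comparisons descriptive.

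Two further defences carry some weight. The permutation test does not rely on the Poisson variance and could expose a success that rests only on a narrow interval, but it cannot change the declared outcome. The statistical analysis plan was not available and may specify a scaled or robust variance; naming a Poisson distribution does not strictly exclude one. The protocol nevertheless fixes the switch itself, and on a literal reading the interval is the model-based one.

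**Conclusion.** The point holds in conditional form. If the fallback is used for the primary endpoint while overdispersion of 1.8 is present, the interval that decides success is about 25% too narrow, and one-sided false success is about 13% instead of 6.5%. The result rests on the factor assumed in Section 11.4, on an unscaled reading of the fallback, and on a large-sample approximation that simulation supports.

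It does not show that the trial's overall error rate is wrong, and it is no objection to Negative Binomial regression as the primary model. It should be fixed, but it is not a critical flaw: the contingency is rare, yet the rule written for it conflicts with the protocol's own variance assumption.

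**What to change.** Replace the fallback sentence in Section 11.8 with wording such as: *Should the Negative Binomial fit fail to converge, a log-linear Poisson model with the same covariates and offset and a robust (sandwich) or Pearson-scaled variance will be fitted, and the 87% and 95% CIs will be taken from it.* Choose one of the two variance estimators in advance, and apply the rule wherever the primary model is reused.

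Country need not be dropped. It is a minimisation factor (Section 6.2.2.2.1), and removing it would change the primary model without being needed to correct the variance.

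The cost is one sentence and one programming option. The sample size is unaffected, and without overdispersion the corrected interval is essentially the ordinary Poisson one.
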